7.5.7 Safety Monitoring Rule for Documented Severe Hypoglycemia

Classification of Hypoglycemia

1. **Alert value for hypoglycemia**
≤70 mg/dL (≤3.9 mmol/L) plasma concentration
2. **Severe hypoglycemia**
Requires assistance of another person to actively administer carbohydrates, glucagon, or take other corrective actions. Plasma glucose concentrations may not be available during an event. Neurological recovery following plasma glucose levels returning to normal is considered sufficient evidence that an event was induced by low plasma glucose concentration.
3. **Documented symptomatic hypoglycemia**
Typical hypoglycemia symptoms accompanied by measured plasma glucose ≤70 mg/dL (≤3.9 mmol/L).
4. **Asymptomatic hypoglycemia**
Not accompanied by typical hypoglycemia symptoms but with measured plasma glucose ≤70 mg/dL (≤3.9 mmol/L).
5. **Probable symptomatic hypoglycemia**
Typical hypoglycemia symptoms not accompanied by plasma glucose determination but likely caused by plasma glucose ≤70 mg/dL (≤3.9 mmol/L).

A **documented severe hypoglycemic event** is defined as one in which the patient requires assistance of another person to obtain treatment for the event and has a plasma glucose level ≤70 mg/dL (≤3.9 mmol/L). The rescue treatment of hypoglycemia may include IV glucose or buccal or intramuscular glucagon. The definition of severe symptomatic hypoglycemia includes all episodes in which neurological impairment was severe enough to prevent self-treatment and which were thus thought to place patients at risk for injury to themselves or others. Note that “requires assistance” means that the patient could not help himself or herself. Someone being kind that assists spontaneously the patient when not necessary does not qualify as “requires assistance.” Severe hypoglycemia will be qualified as a SAE only if it fulfills SAE criteria.

If a patient presents with symptoms of hypoglycemia, the Investigator will need to take immediate action to confirm the patient's glucose level and treat the patient accordingly. Patients must be instructed on the monitoring and management of hypoglycemic episodes at the Baseline Visit. Instructions should be provided to all patients on the appropriate use of a glucose meter. The experience of hypoglycemia may vary greatly from patient to patient. However, there are certain classical signs and symptoms, of which patients should be aware as a clue that their blood glucose may be low. Common symptoms include headache, heart pounding, confusion, disorientation, numbness or tingling, pale skin, shakiness or tremulousness, increased appetite, anxiousness or nervousness, lightheadedness or dizziness, sweating, and weakness. Many of these symptoms are listed in the diary provided to patients. These diaries will be used only to assist the investigator in assessing the event. Appropriate source documentation should capture the necessary information on the event with the aid of the diaries. Patients must be given adequate instructions on the use of the diaries.

If patients suspect they might be having a hypoglycemia reaction, they should check their blood glucose using their meters as soon as possible, before treatment if possible, provided they feel it is safe to do so. If there is doubt about safety they should treat the event first, using some sugar, milk, or juice for example, then obtain and record a blood glucose value as soon as possible thereafter. The time and nature of treatment should be noted, and especially if any blood glucose result was before or after treatment. It would be helpful for the patient to note if a contributory factor (eg, missed or reduced meals, unaccustomed physical activity) occurred earlier in the day of the event.

Doses of insulin and sulfonylureas may be reduced at the Investigator's discretion for hypoglycemia. Doses of other diabetes medications (e.g. metformin) should not be changed.

7.5.8 Monitoring Rule for Hyperglycemia

Assessment for rescue will be performed at each "visit" (including both telephone contacts and in-person visits). Routine fasting SMPG and central lab alerts on FPG (and HbA1c after week 12) are set up to ensure that glycemic parameters remain under predefined thresholds values. If one fasting SMPG value exceeds the specific glycemic limit on one day, the patient checks it again during the two following days. If all the values in three consecutive days exceed the specific limit, the patient should contact the investigator and a central laboratory FPG measurement (and HbA1c after week 12) is performed.

The threshold values are defined as follows, depending on study period:

- From baseline visit to week 12 (*including value at week 12*): FPG >270 mg/dL (15.0 mmol/L)
- From week 12 to week 24 (*including value at week 24*): FPG >240 mg/dL (13.3 mmol/L) or HbA1c >9% (for patients with baseline HbA1c <8%) and HbA1c increase of more than 1% from baseline (for patients with baseline HbA1c ≥8%).
- From week 24 up to week 68 : HbA1c >9% (for patients with baseline HbA1c <8%) and HbA1c increase of more than 1% from baseline (for patients with baseline HbA1c ≥8%).

In case of FPG/HbA1c above the threshold values, the investigator should ensure that no reasonable explanation exists for insufficient glucose control and in particular that:

- Plasma glucose was actually measured in the fasting condition (i.e. after at least 10 hours fast)

- Absence of intercurrent disease which may jeopardize glycemic control. In case of an emergency (e.g., surgery, infection), the investigator can take appropriate measures for glycemic control. If the measure does not exceed 7 days, then it will not be considered a rescue. If the measure lasts beyond 7 days then it will be treated as a rescue.
- Compliance to treatment is appropriate
- Compliance to diet and lifestyle is appropriate

If any of the above can reasonably explain the insufficient glycemic control, the investigator should undertake appropriate action, i.e.

- Investigation and treatment of intercurrent disease (to be reported in AE/concomitant medication parts of the e-CRF),
- Stress on the absolute need to be compliant to treatment,
- Organize a specific interview with a Registered Dietician or other qualified nutrition professional and stress on the absolute need to be compliant to diet and lifestyle recommendations,
- Schedule a FPG/HbA1c assessment at the next visit.

If none from the above-mentioned reason can be found, or if appropriate action fails to decrease FPG/HbA1c under the threshold values, rescue medication may be introduced at the investigator discretion and according to local guidelines.

Any patient who discontinues early from the placebo-controlled or OLE periods will be encouraged to attend a final in-person follow-up visit (Week 80 visit assessments per Appendix A) approximately 12 weeks after their last dose of Study Drug. If the patient declines or is unable to participate in the above, a home nurse visit for safety/efficacy labs.

If possible, an in-person visit for all assessments for primary and secondary efficacy and safety parameters planned in final primary endpoint assessment visit will be performed before adding the rescue medication. If an in-person visit cannot be conducted in a timely fashion, a home nurse visit for safety/efficacy labs will be attempted. If rescue medication is required, patients will continue the study treatment and remain in the study, although planned tests that will be affected by the use of rescue medication may be cancelled.

7.5.9 Acute Pancreatitis

If a patient has an episode of acute pancreatitis, dosing with study drug should be suspended temporarily until the patient is clinically stable. The suitability of the patient for continued dosing and the need for any modification to the treatment schedule will be determined by the Investigator, with consultation with the Sponsor Medical Monitor as needed.

7.6 Stopping Rules

For the purposes of stopping rules, baseline is defined as the average of Day 1 pre-dose assessment and the last measurement prior to Day 1. Prior to discontinuing study drug in any patient, the Investigator will consult with the Sponsor Medical Monitor when possible.

7.6.1 Stopping Rules for Liver Chemistry Elevations

In the event of confirmed laboratory results meeting the following criteria, **and the event is without an alternative explanation** as determined by the Investigator, dosing of a patient with Study Drug (ISIS 304801) will be stopped permanently:

1. ALT or AST > 8 x ULN, which is confirmed
2. ALT or AST > 5 x ULN, which is confirmed and persists for ≥ 2 weeks
3. ALT or AST > 3 x ULN (or the greater of 2 x baseline value or 3 x ULN if the baseline value was > ULN), which is confirmed **and** total bilirubin > 2 x ULN or INR > 1.5
4. ALT or AST > 3 x ULN (or the greater of 2 x baseline value or 3 x ULN if the baseline value was > ULN), which is confirmed, and the new appearance (i.e., onset coincides with the changes in hepatic enzymes) of fatigue, nausea, vomiting, right upper quadrant pain or tenderness, fever, rash, or eosinophilia (> ULN) felt by the Investigator to be potentially related to hepatic inflammation

7.6.2 Stopping Rules for Renal Function Test Results

In the event of persistent changes that are observed over 2 consecutive weeks, for **any** of the criteria below, dosing of a patient with Study Drug (ISIS 304801 or placebo) may be stopped temporarily:

1. Quantitative total urine protein measurement of > 3.5 g/24 hours
2. Estimated creatinine clearance calculated according to the formula of Cockcroft and Gault ≤ 40 mL/min that is confirmed by a 24 hour urine collection

The possible dosing re-initiation or follow-up schedule for any events meeting either of these criteria will be determined by the Investigator, in consultation with the Sponsor Medical Monitor as needed.

7.6.3 Stopping Rule for Platelet Count Results

In the event of a confirmed platelet count less than 75,000/mm³ that is associated with major bleeding or clinically relevant non-major bleeding (defined below⁵³), dosing of a patient with study drug (ISIS 304801 or placebo) will be stopped permanently. The follow-up schedule for any events meeting this stopping criterion will be determined by the Investigator in consultation with the Sponsor Medical Monitor as needed.

In the event of any platelet count less than 25,000/mm³, or a platelet count less than 50,000/mm³ that occurs while the patient is on dosing at 300 mg every two weeks or 150 mg every week then dosing of a patient with Study Drug (ISIS 304801 or placebo) will be stopped permanently. Platelet count will be monitored daily until 2 successive values show improvement then monitored every 2-3 days until 2 successive values are > 75kmm³, then monitored every 1 week.

Administration of steroids is recommended for patients whose platelet count is less than $\leq 50K/mm^3$. Recovery in platelet count may be accelerated by administration of high dose steroids. Treatment guidelines for immune thrombocytopenia (Provan et al.; 2010) recommend Dexamethasone 40 mg daily for 4 days every 2-4 wk for 1-4 cycles; Prednis(ol)one 0.5-2 mg/kg/d for 2-4 weeks then taper; or Methylprednisolone 30 mg/kg/day for 7 days (**note:** may require continuation with oral steroids after methyl prednisolone).

In the event of a confirmed platelet count less than 75,000/mm³, and in the absence of major bleeding or clinically relevant non-major bleeding (defined below⁵³), dosing of a patient with study drug (ISIS 304801 or placebo) will be suspended temporarily until the platelet count has recovered to $\geq 100,000/mm^3$. If dosing is continued it should be at a reduced dose frequency of 300 mg every two weeks or a reduced dose of 150 mg per week. The suitability of the patient for continued dosing and the need for any modification to treatment

schedule (refer to Section 7.7) will be determined by the Investigator (in consultation with the Ionis Medical Advisor as needed) and will be based on factors such as the original rate of decline in the patient’s platelet count, whether any bleeding events were experienced by the patient, and the speed of recovery of platelet count upon holding of dosing.

If after the first dosing re-challenge the platelet count again falls below 50,000/mm³, then dosing of the patient must be held until the platelet count again returns to at least 100,000/mm³. The suitability of the patient for continued dosing and the need for any further modification to treatment schedule or dose (refer to Section 7.7) will be re-examined by the Investigator (in consultation with the Sponsor Medical Monitor as needed) based on (at least) the factors mentioned above.

If after the second re-challenge the platelet count falls below 50,000/mm³ and is subsequently confirmed (see Section 7.5), dosing with Study Drug will be stopped permanently. The follow-up schedule for any events meeting this stopping criterion will be determined by the Investigator (in consultation with the Sponsor Medical Monitor as needed).

Following rechallenge platelet count should be tested every week until count is stable.

Any unreportable platelet count result must be rechecked and determined not to have met a stopping rule before dosing can continue.

If there is no reportable platelet count within 14 days of the last platelet count, the investigator will contact the patient to hold dosing until a new platelet count is obtained and reviewed.

Definition of Major Bleeding Events^{s3}:

1. Fatal bleeding, and/or
2. Symptomatic bleeding in a critical area or organ, such as intracranial, intraspinal, intraocular, retroperitoneal, intraarterial or pericardial, or intramuscular with compartment syndrome, and/or
3. Bleeding causing a fall in hemoglobin level of 20.0 g/L (1.24 mmol/L) or more within 24 hours, or leading to transfusion of two or more units of whole or red cells

Definition of Clinically Relevant, Non-Major Bleeding Events^{s3}:

1. Multiple-source bleeding
2. Spontaneous hematoma >25 cm²
3. Excessive wound hematoma (not injection site related)
4. Macroscopic hematuria (spontaneous or lasting >24 hours if associated with an intervention)
5. Spontaneous rectal bleeding; epistaxis, gingival bleeding, hemoptysis, hematemesis
6. Bleeding after venipuncture for >5 minutes

Actions in Patients With Low Platelet Count

Platelet count	Dosing Rules	Monitoring Rules
Normal range, >140K/mm ³	No action	Monitor every week unless otherwise specified

100K/mm ³ - 140K/mm ³	Weekly 300 mg study drug administration	Monitor every 1 week unless otherwise specified Obtain additional lab tests if 2 occurrences of platelet count 100 K/mm ³ -- 140K/mm ³ or 1 occurrence of platelet count ≤ 100K/mm ³ **
75K/mm ³ - 100K/ mm ³	Permanently reduce dose frequency to 300 mg every 2 weeks	Monitor every 1week unless otherwise specified Obtain additional lab tests if 1 occurrence of platelet count ≤ 100K/mm ³ **
50K/mm ³ - 75K/mm ³	If occurs while on dose of 300 mg every 2 weeks or 150 mg every week then permanently discontinue Study Drug, otherwise dose pause. When platelet count returns to >100K/mm ³ restart dosing at dose frequency of 300 mg every 2 weeks or 150 mg weekly ₁ (in consultation with the Ionis Medical Advisor as needed).	Monitor every 2-3 days until two successive values are > 75K/mm ³ then monitor every 1 week Consider discontinuation of antiplatelet/agents/NSAIDS/anticoagulant medication Obtain additional lab tests if 1 occurrence of platelet count ≤ 100K/mm ³ **
≤ 50 K/mm ³	Permanently discontinue Study Drug	Monitor daily until 2 successive values show improvement, then monitor every 2-3 days until 2 successive values are > 75K/ mm ³ . Patient should be evaluated by a hematologist to provide diagnostic and therapeutic management Steroids recommended*. It is strongly recommended that, unless the patient has a medical contraindication to receiving glucocorticoids, the patient receives glucocorticoid therapy to reverse the platelet decline. Monitor triglyceride levels weekly and continue AE monitoring during steroid therapy. Discontinue antiplatelet agents/NSAIDS/anticoagulant medication while platelet count <50K/mm ³ if

		possible Obtain additional lab tests if 1 occurrence of platelet count $\leq 100\text{K}/\text{mm}^3$ **
--	--	---

*Recovery in platelet count may be accelerated by administration of high dose steroids. Treatment guidelines for immune thrombocytopenia (Provan et al. 2010) recommend Dexamethasone 40 mg daily for 4 days every 2-4 weeks for 1-4 cycles; Prednis(ol)one 0.5-2 mg/kg/d for 2-4 weeks then taper; or Methylprednisolone 30 mg/kg/day for 7 days (**note:** may require continuation with oral steroids after methyl prednisolone)

**See Appendix J

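### Section 7.6.3 is inconsistent on whether study drug may be restarted after a platelet count of 25K to 50K without bleeding, and on a reduced regimen up to 75K

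*Combined protocol and SAP*

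**What the plan says.** All counts below are per mm³. A reduced regimen means 300 mg every other week or 150 mg weekly.

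The text of Section 7.6.3 has these rules:

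- With major or clinically relevant non-major bleeding, a confirmed count below 75K is a permanent stop.
- A permanent stop also applies "In the event of any platelet count less than 25,000/mm³", and for "a platelet count less than 50,000/mm³ that occurs while the patient is on dosing at 300 mg every two weeks" or on 150 mg weekly.
- Without such bleeding, a confirmed count below 75K means dosing "will be suspended temporarily until the platelet count has recovered to" at least 100K. No lower limit is stated. On restart, "If dosing is continued it should be at a reduced dose frequency of 300 mg every two weeks" or 150 mg weekly.
- "If after the first dosing re-challenge the platelet count again falls below 50,000/mm³, then dosing of the patient must be held" until the count is back to at least 100K. The Investigator then re-examines "The suitability of the patient for continued dosing and the need for any further modification to treatment schedule or dose".
- "If after the second re-challenge the platelet count falls below 50,000/mm³ and is subsequently confirmed", the stop is permanent.

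The table at the end of 7.6.3 has no re-challenge steps. Its row for 50K or less is an unconditional permanent stop. Its 50K–75K row is a permanent stop on a reduced regimen and otherwise a pause, with a reduced-regimen restart above 100K.

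Other sections touch the same decision. Section 7.5.3 refers to the table for platelet actions. Section 7.5 makes confirmed stopping criteria permanent and bars re-dosing until the retest is available. Section 7.7 requires accordance with both 7.6.3 and the table. Section 7.8, item 2, lists meeting a stopping rule as a ground for withdrawal.

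**The concern.** An investigator whose patient recovers from a count of, say, 40K has to decide whether the drug may be given again. One part of 7.6.3 permits this after review and another forbids it. Two patients with the same count and dosing history could be handled differently, each in line with some part of the protocol.

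The decision matters for safety. At these counts the section treats the patient as needing active management: "Administration of steroids is recommended for patients whose platelet count is less than" or equal to 50K, and the table adds evaluation by a hematologist. Platelets are counted weekly throughout. In the extra 12 months of open-label dosing, Section 6.3.7 moves that monitoring to local providers without home nurse visits, so the rule should be readable in only one way.

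**Working it through.** No arithmetic applies. The check lists every rule in 7.6.3 that covers a given count and dosing state, without major or clinically relevant non-major bleeding, and compares the required actions.

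| Count | Dosing state | Text of 7.6.3 | Table in 7.6.3 | Agree? |
|---|---|---|---|---|
| Below 25K | Any | Permanent stop | Permanent stop | Yes |
| 25K to <50K | 300 mg weekly | Suspend; reduced restart possible at ≥100K | Permanent stop | No |
| 25K to <50K | Reduced regimen, no earlier re-challenge | Permanent stop | Permanent stop | Yes |
| 25K to <50K | After first re-challenge | Permanent stop in one paragraph; hold with possible restart in another | Permanent stop | No |
| 25K to <50K | After second re-challenge | Permanent stop | Permanent stop | Yes |
| Exactly 50K | 300 mg weekly | Suspend | Falls in two rows: pause and permanent stop | No |
| >50K to <75K | 300 mg weekly | Suspend | Pause | Yes, except restart at ≥100K against >100K |
| >50K to <75K | Reduced regimen | Suspend | Permanent stop | No |

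The suspension sentence has no dose limit, so read literally it also covers counts below 25K and counts below 50K on a reduced regimen. The table above lets the specific permanent-stop sentence displace it there. That is the reading most favorable to the plan.

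**300 mg weekly, 25K to below 50K.** The text confines its bleeding-free permanent stop to below 25K at any dose and below 50K on a reduced regimen. If the table's stop at 50K or less on any dose governed, both conditions would be redundant. The text therefore treats full-dose patients in this range differently from the table.

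**After the first re-challenge.** The text directs that a restart be on a reduced regimen. A count below 50K on that regimen is a permanent stop under the text's own earlier sentence and under the table. A patient stopped on that basis could never reach the second re-challenge for which the text provides. The word for recurrence in the first re-challenge rule also suggests that a patient already below 50K had been restarted, which the table forbids. Preferring the specific rule to the general one does not settle this, because the re-challenge paragraph is itself specific to its stage.

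**Reduced regimen, above 50K and below 75K.** A patient can be here without any suspension, because the table moves patients at 75K–100K permanently to 300 mg every other week. The text then suspends while the table stops for good.

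**Row edges.** Exactly 50K and exactly 75K each fall in two rows of the table.

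**The case against.** The strongest defense is that the protocol already leans one way. Section 7.5.3 names the table as the place to find platelet actions, and Sections 7.5, 7.7 and 7.8 favor the stricter action. A permanent stop also breaches nothing: the re-challenge paragraph requires a hold and a review, never a restart, and the suspension paragraph speaks only of what happens if dosing continues. The clash is between a discretionary permission and a prohibition, not between two incompatible commands.

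Most of this stands, and it lowers the weight of the point. It does not remove it. None of those sections is a precedence clause, and Section 7.7 asks for accordance with both sources, which is impossible for a patient restarted under the re-challenge paragraph. An investigator following that paragraph would re-dose a patient whom the table bars.

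A second objection is that the reduced restart regimen is worded as a recommendation, so a re-challenge could be at full dose. The conflict inside the text would then fall away for that patient, but the conflict with the table would remain.

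A reader might also infer that drug could continue through a very low count. The documents do not support that: every reading stops dosing at once, and below 25K the specific text rule and the table agree on a permanent stop. Nor do they support extending the point to the renal and hypoglycemia rules in 7.6.2 and 7.6.4. No defect in those is shown here.

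**Conclusion.** The inconsistency is real and should be fixed. It covers three situations without major or clinically relevant non-major bleeding: 25K to 50K on 300 mg weekly, 25K to below 50K after the first re-challenge, and above 50K but below 75K on a reduced regimen. It concerns only a later restart, after recovery to about 100K and an Investigator review, with weekly counts afterwards.

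No number of affected patients can be given. Section 2.3.4 reports only a mild platelet decrease in Phase 2, and the trial aims for 10 completers. A reader might infer that the primary comparison is compromised. The documents do not support that, since Section 5.2 analyzes all available data regardless of adherence. The point rests on patient safety and consistent conduct alone.

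The conflict inside the text assumes that re-challenge is on a reduced regimen, as 7.6.3 recommends. The conflicts between text and table need no such assumption.

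**What to change.** State in 7.6.3 that the table governs, and align the text to it:

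- Permanent stop at 50K or less on any dose, and below 75K on a reduced regimen.
- Keep the permanent stop for a confirmed count below 75K with major or clinically relevant non-major bleeding.
- Limit temporary suspension to counts above 50K and below 75K on 300 mg weekly without such bleeding. Restart is at a reduced regimen once the count is at least 100K, with that one threshold in both text and table.
- Delete the two paragraphs on dosing after the first and second re-challenge. Keep the weekly platelet testing after a restart.
- Make the table rows exclusive at 50K and 75K.
- Hold dosing while any confirmation under Section 7.5 is pending.

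Leave the general sentence in 7.5 unchanged; this point gives no reason to edit it for the renal or hypoglycemia rules. Aligning the table to the text would also give a single rule, but it would allow re-dosing after counts at which the section recommends steroids, and Section 7.5.3 already directs staff to the table.

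The cost is a wording amendment, with no extra tests, visits or patients. The downside is clinical: a patient who recovers after a count of 50K or less, or after a count below 75K on a reduced regimen, loses a discretionary re-challenge. The table already makes that choice.

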6.2.2.5 Study Drug Administration

For each individual patient, Study Drug will be administered SC as a single 1.5 mL injection once weekly for Weeks 1-68. Self-administration will be allowed after appropriate training of the patient and/or caregiver. Patients should receive 1 dose per week, with weeks always defined relative to Study Day 1. For example, if a patient receives the first dose on a Monday, subsequent doses should be given on Mondays, if possible. If a patient misses an injection, or if dosing on the usual day is not possible, the patient can reschedule the injection provided that 2 doses are administered at least 2 days apart.

Every effort should be made to ensure the previous week's dose is given 7 days prior to a scheduled clinic visit. Subjects will not be removed from the study because of missed dosing; however, subjects missing more than 2 doses before Week 13 may not be evaluable for the primary endpoint.

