7.7 Adjustment of Dose and/or Treatment Schedule

Dose adjustments for platelet count reduction must be made in accordance with Section 7.6.3 and Table (above).

Other dose adjustments, including dose interruptions, and/or decreasing the dose frequency will be allowed for safety or tolerability, after consultation with the Ionis Medical Advisor if possible. Dose adjustments should not occur unless absolutely necessary prior to the primary analysis time point (Week 12).

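### In the Section 7.6.3 platelet table, the 100K-140K and 75K-100K rows do not say whether they cover patients already on a reduced regimen or on a pause, and read literally they conflict with neighbouring rules

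*Combined protocol and SAP*

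**What the plan says.** The table in Section 7.6.3 assigns a dosing rule to each band of platelet count:

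- **Above 140K:** no action.
- **100K-140K:** "Weekly 300 mg study drug administration".
- **75K-100K:** "Permanently reduce dose frequency to 300 mg every 2 weeks".
- **50K-75K:** "If occurs while on dose of 300 mg every 2 weeks or 150 mg every week then permanently discontinue Study Drug"; otherwise pause. Once the count is back above 100K, "restart dosing at dose frequency of 300 mg every 2 weeks or 150 mg weekly".
- **50K or below:** permanent discontinuation.

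The text of the same section covers a confirmed count below 75,000/mm³ without major or clinically relevant bleeding. Dosing is suspended until the count is at least 100,000/mm³. After that, dosing may resume only on a reduced regimen, again 300 mg at two-week intervals or 150 mg weekly. Suitability for further dosing, and any change of schedule, are left to the investigator.

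Section 7.7 requires platelet-related dose adjustments to follow both Section 7.6.3 and its table. Section 6.4.5 has platelets checked every week for the whole study.

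**The concern.** Only the 50K-75K row asks which regimen the patient is on. The two rows above it are triggered by the current count and name a regimen without stating whom they cover. Yet patients whose dosing has already been changed will have counts in exactly those bands: a pause ends only at about 100K, and a recovery from below 75K to 100K passes through 75K-100K.

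This is a safety rule for a recognised effect of the drug, since Section 2.3.4 reports a mild platelet decrease in the Phase 2 studies. The table is consulted at every weekly count. If two binding instructions disagree, two readers can act differently on the same patient, and neither has departed from the protocol.

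**Working it through.** The plan gives no figure of its own on this point, so there is none to reproduce. The check converts each regimen to a common scale and then applies the rows literally to patients whose dosing has already been changed.

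**Step 1: mean weekly amount.** Formula: mg per injection ÷ weeks between injections. The regimens are those named in the Section 7.6.3 table and text.

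- 300 mg weekly: 300 ÷ 1 = 300 mg/week
- 300 mg every 2 weeks: 300 ÷ 2 = 150 mg/week
- 150 mg weekly: 150 ÷ 1 = 150 mg/week
- Ratio of the first to either of the others: 300 ÷ 150 = 2

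**Step 2: rows set against the neighbouring rules.**

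| Case | Patient's state | Count now | Row for that count | Other rule that applies | Mean mg/week |
|---|---|---|---|---|---|
| 1 | Paused after 50K-75K, restarting | 100K-140K | 300 mg weekly | 50K-75K row and Section 7.6.3 text: 300 mg every 2 weeks or 150 mg weekly | 300 vs 150 |
| 2 | Frequency reduced at 75K-100K | 100K-140K | 300 mg weekly | 75K-100K row: the reduction is permanent | 300 vs 150 |
| 3 | Paused after 50K-75K | 75K-100K | 300 mg every 2 weeks | 50K-75K row and Section 7.6.3 text: stay paused until 100K | 150 vs 0 |

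**Step 3: can the cases be avoided in practice?** Case 1 cannot be avoided at a restart count between just above 100K and 140K, because the restart condition and the 100K-140K row share that range. It recurs at each later weekly count in the band. Case 2 arises whenever a patient reduced at 75K-100K recovers into the next band. Case 3 arises whenever a count is taken while a paused patient is between 75K and 100K. The table's own monitoring column asks for counts every 2-3 days until two successive values exceed 75K, and weekly after that.

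**Step 4: is there a rule of precedence?** Section 7.7 names the section and the table together. Neither place says that one governs the other, or that one row governs another.

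**The case against.** The best defence is that a sensible reader would not be misled. A later count cannot undo a permanent reduction without emptying the word of meaning. The 50K-75K row itself names the regimen for a count that has returned above 100K. The text says that resumed dosing should be at a reduced frequency or dose, and Section 7.7 requires the table to be read with that text. On this view the 100K-140K row is for patients never reduced, and the 75K-100K row is for patients currently being dosed. The investigator's discretion covers the rest.

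Much of this stands. It shows that a coherent reading exists, so a reader who infers that the protocol actually returns reduced patients to weekly 300 mg goes further than the documents allow. That is one literal reading, and other wording points against it.

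The defence does not remove the point. The limited scope it needs is not written in either row. The drafting is also mixed: the row above 140K asks for no action and so leaves any regimen in place, whereas the 100K-140K row names a specific one. The 50K-75K row shows that the table conditions on regimen where its authors meant it to. The investigator's discretion in the text concerns patients with a confirmed count below 75,000/mm³. It does not reach a patient reduced at 75K-100K without a pause (case 2).

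Four further inferences are tempting and are not supported:

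- *The 75K-100K row contradicts the rules for a patient already on a reduced regimen, because it is no reduction.* The weekly amount does stay at 150 mg. But no rule asks for a further step in that band, and the row speaks of frequency. This is a gap, not a contradiction.
- *Section 6.2.2.5 conflicts by prescribing the drug "as a single 1.5 mL injection once weekly for Weeks 1-68".* That is the default schedule, and Section 7.7 provides for adjusting it.
- *A 300 mg syringe makes the 150 mg option a two-fold dosing risk.* The documents do not describe how 150 mg would be given, so a full-syringe error is hypothetical.
- *The efficacy or pharmacokinetic results are blurred.* Nothing shows how many patients would be affected or that the dose given would go unrecorded, and Section 5.2 plans additional analyses of adherence.

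**Conclusion.** The point holds as a conflict of stated rules. Neither the 100K-140K row nor the 75K-100K row states how it applies to a patient already on a reduced regimen or on a pause. Read literally, they disagree with neighbouring rules in three situations. In two of these the mean weekly amount differs two-fold (300 against 150 mg). In the third the choice is between dosing and no dosing. Text and table bind together, and no order of precedence is given.

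The conclusion rests on the wording alone. It does not assume that any patient would be dosed in one way or the other, and the documents give no basis for estimating how often the three situations would occur. It takes no position on which regimen or threshold is right.

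**What to change.** Reconcile the passages. For the 100K-140K row and the 75K-100K row, state explicitly how each applies to (a) a patient already on a reduced regimen and (b) a patient on a dosing pause. The 50K-75K row already conditions on current regimen and can serve as the pattern. The same edit can settle whether a pause ends above 100K, as in the table, or at 100,000/mm³ and over, as in the text. The sponsor decides which rule applies in each case.

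The cost is a change of wording to two table rows and, if the threshold is aligned, to one further phrase. It needs no extra tests, visits or patients.
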